3.5. ADVERSE EVENT EVALUATION AND REPORTING

3.5.1. ADVERSE EVENTS

AE definitions will be consistent with the "Note for Guidance on clinical safety data management: definitions and standards for expedited reporting" (International Conference on Harmonization [ICH] topic E2A).

An AE is any untoward medical occurrence in a clinical study subject administered a medicinal (investigational or non-investigational) product. An AE does not necessarily have a causal relationship with the treatment. An AE can therefore be any unfavorable and unintended sign (including an abnormal finding), symptom, or disease temporally associated with the use of a medicinal (investigational or non-investigational) product, whether or not considered related to that medicinal (investigational or non-investigational) product.

This includes any occurrence that is new in onset or aggravated in severity or frequency from the baseline condition, or abnormal results of diagnostic procedures, including laboratory test abnormalities.

In differentiating between medical history and AEs, the following points will be considered:

- Conditions that started before signing of informed consent and for which no symptoms or treatment are present up to the timing of signing of informed consent are recorded as medical history (e.g., seasonal allergy without acute complaints).
- Conditions that started before signing of informed consent and for which symptoms or treatment are present after signing of informed consent, but with unchanged severity, are recorded as medical history (e.g., allergic pollinosis).
- Conditions that started or deteriorated after signing of informed consent will be documented as AEs.

A TEAE is any AE temporally associated with the use of study drug, whether considered related to the study drug or not.

It is the responsibility of the Investigator to collect all AEs (both serious and non-serious) derived by spontaneous, unsolicited reports of subjects, by observation, and by routine open questioning (e.g., "How have you felt since I saw you last?"; "Is there anything new that you wish to discuss?").

All AEs will be assessed by the Investigator and recorded in the patient medical records and on the AE eCRF page. AE entry should indicate time of onset and end time and rating of the

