2.1.4.1 Adverse events variables

Adverse event observation period

- On-study adverse events are adverse events that developed or worsened or became serious during the on-study period
- Treatment-emergent adverse events are adverse events that developed or worsened or became serious during the treatment-emergent adverse event period

All adverse events (including serious adverse events (SAE)) will be coded to a lower-level term (LLT), preferred term (PT), high-level term (HLT), high-level group term (HLGT), and associated primary system organ class (SOC) using the version 22.0 of Medical Dictionary for Regulatory Activities (MedDRA).

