2.4.5.1 Analyses of adverse events

Generalities

The primary focus of adverse event reporting will be on treatment-emergent adverse events. Pretreatment and posttreatment adverse events will be described separately.

If an adverse event date/time of onset (occurrence, worsening, or becoming serious) is incomplete, an imputation algorithm will be used to classify the adverse event as pretreatment,

treatment-emergent, or posttreatment. The algorithm for imputing date/time of onset will be conservative and will classify an adverse event as treatment emergent unless there is definitive information to determine it is pretreatment or posttreatment. Details on classification of adverse events with missing or partial onset dates are provided in [Section 2.5.3](#).

Adverse events (AEs) will be placed into analysis periods according to their start date (time). The AE will only be presented in the analysis period during which it started, ie, period start date (time) \leq AE start date (time) \leq period stop date (time). There will be no imputation of other missing date (time) fields, nor of the missing parts of other partially known date (time) fields. When needed (e.g., an incomplete date (time) leads to a double phase allocation), the following rules will be applied: adverse events will be allocated on all analysis levels (ie, for analysis periods and subperiods, see [Section 2.5.4](#)) according to their start date (time). In case the adverse event (AE) start date(time) is incomplete, the allocation will be done according to the available parts of the AE start date(time) and taking into account the AE end date(time) (ie, the AE start date(time) cannot be later than the AE end date(time)):

- When, due to missing date (part) an allocation needs to be made to an analysis period, the AE will be allocated to the treatment phase and not off-treatment phase (worst-case allocation).
- When an allocation needs to be made to a specific recurrence period, the AE will be allocated to the first recurrence period.
- When an allocation needs to be made within a recurrence period, the event will be allocated to the daily PE subperiod.

Tables on the recurrence population will include only adverse events that occurred during the recurrence period, treatment-emergent (for patients who received the IMP) and non-treatment emergent (for patients who did not received the IMP).

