2.5.4 Windows for time points

The following analysis periods and phase are defined for this study for the Q6M FU visits and the recurrence period.

Table 1 – Analysis phases and periods for the recurrence period- Caplacizumab treated patients

Phase	Period	Subperiod	Start date	End date
Recurrence episode x	Treatment	Daily PE	Recurrence visit date of the recurrence episode	End date of the daily plasma exchange in the recurrence episode
		Post-daily PE	End date of daily plasma exchange in the recurrence episode + 1 day	End date of the treatment period in the recurrence episode
	Follow-up		End date of treatment period + 1 day	Recurrence follow-up visit date

Table 2 – Analysis phases periods for the recurrence period – non-treated patients

Phase	Period	Subperiod	Start date	End date
Recurrence episode x	No-treatment	Daily PE	Recurrence visit date in the recurrence episode	End date of daily plasma exchange in the recurrence episode
	Follow-up		End of daily plasma exchange in the recurrence episode + 1 day	Recurrence follow-up visit date

Table 3 – Analysis phases and periods for the Q6M FU visits

Phase	Period	Subperiod	Start period	End period
Observation			Screening/baseline visit	End of participation to the trial

Note that the last analysis period in case of early termination will always be ended by the trial termination date.

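### The SAP defines worsening on caplacizumab as treatment-emergent but places adverse events by start date, so a single-record event that began before the recurrence visit can miss that episode's TEAE tables

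*SAP*

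**What the plan says.** SAP 2.1.4.1 gives the definition: "Treatment-emergent adverse events are adverse events that developed or worsened or became serious during the treatment-emergent adverse event period". SAP 2.1.4 sets that period, within a recurrence treated with study drug, as first dose to last dose plus 30 days.

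SAP 2.4.5.1 gives the placement rule. Events go into analysis periods by start date, and "The AE will only be presented in the analysis period during which it started". A formula follows: the AE start must lie between the start and stop of the period. The same section adds: "Tables on the recurrence population will include only adverse events that occurred during the recurrence period". TEAE summaries for the recurrence population are made by analysis period. Table 1 in SAP 2.5.4 opens the first period of a treated episode at the "Recurrence visit date of the recurrence episode".

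Three other texts bear on the point:

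- SAP 2.4.5.1 widens the meaning of onset, but in a rule for incomplete dates: "If an adverse event date/time of onset (occurrence, worsening, or becoming serious) is incomplete, an imputation algorithm will be used". Where such a date leaves the period open, the event goes to the treatment phase as the worst case.
- SAP 2.4.5.1 derives AE onset day from the AE start date alone.
- Protocol 3.5.1 says of the AE definition: "This includes any occurrence that is new in onset or aggravated in severity or frequency from the baseline condition". To separate AEs from medical history it adds: "Conditions that started or deteriorated after signing of informed consent will be documented as AEs".

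**The concern.** The definition looks at when an event developed, worsened or became serious. The placement rule looks only at when it started. For most events these dates coincide. They differ for an event already present when the patient comes in with a recurrence that then gets worse on drug.

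This matters because Protocol 1.2.5 names increased bleeding as the main safety finding with caplacizumab, and the safety of repeated use is a study objective. Bleeding is also among the presenting symptoms of a recurrence (Protocol 3.4.3, SAP 2.1.3.1.1), so it can precede the visit. The TEAE and bleeding tables for treated recurrences are the natural place to look for worsening on retreatment. The ITO tables are no substitute, because SAP 2.4.5 groups them by caplacizumab exposure in the parent study and not by retreatment in this one.

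**Working it through.** The plan states no figure to reproduce. The check applies its rules to a test case.

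**Assumed days.** Recurrence visit and first dose on Day 1; daily plasma exchange on Days 1 to 6; last dose on Day 36 (6 + 30); recurrence follow-up visit on Day 43 (36 + 7). One AE record has a complete start date 10 days before the visit. The event worsens on Day 5.

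**Definition (SAP 2.1.4 and 2.1.4.1).** The TEAE window is Day 1 to Day 66 (36 + 30). Day 5 lies inside it, so the event is a TEAE.

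**Placement (SAP 2.4.5.1, with Table 1 of 2.5.4).** The test is period start ≤ AE start ≤ period stop. The two overall periods are taken as the span of their parts.

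| TEAE-table period | Days | Start date inside? |
|---|---|---|
| Treatment, daily PE | 1–6 | No |
| Treatment, post-daily PE | 7–36 | No |
| Overall treatment | 1–36 | No |
| Follow-up | 37–43 | No |
| Overall recurrence | 1–43 | No |

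The event is a TEAE that appears in 0 of 5 periods.

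**Two variants of the same event.**

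- The site opens a new record on Day 5. The new start date falls in daily PE, overall treatment and overall recurrence, and the conflict disappears.
- The start date is incomplete and could fall in treatment. The worst-case rule places the event in the treatment phase. A fully dated event is therefore handled less conservatively than a partly dated one.

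**Do the documents decide which record exists?** Protocol 3.5.1 asks each AE entry for onset and end times and for ratings of seriousness, severity and outcome, among other items. It asks for no date of change and does not require a new record when an AE already on file worsens. SAP 2.4.5.1 and 2.5.3 allow for repeat occurrences of one event but do not require them. The question is left to eCRF practice, which the documents do not describe.

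**Can the size be computed?** No. The documents give no frequency for such events. Even the number of patients with a recurrence is loose: Protocol 1.1 cites a median of 18% with a range of 3–84%. If 46 to 92 of the roughly 92 parent-study subjects enrol (an assumption), the range gives 46 × 0.03 = 1.4 to 92 × 0.84 = 77.3, or about 1 to 77 subjects.

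**The case against.** The strongest reply is that the gap may never open in practice. The protocol's AE definition covers aggravation, so a site could enter a worsening as its own occurrence with its own start date. The SAP expects several occurrences per subject and takes the recurrence visit as baseline for recurrence analyses. This stands as a limit on the point: the gap exists only where one record is kept. It does not remove the conflict, because nothing requires a new record, and the protocol's rule on deterioration is anchored at consent and not at first dose.

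A second reply is that the wider meaning of onset in 2.4.5.1 should carry over to the start date. That may well be the intent, and it supports the fix. As written, it sits in the rule for incomplete dates, while the placement formula and the onset-day derivation use the AE start date.

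Third, 2.4.5.1 says events before and after treatment will be described separately. That gives the event a place, but not in the TEAE tables where 2.1.4.1 puts it.

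Fourth, symptoms just before the visit may be recorded only as recurrence information. This is fair, and it means that a separate AE record is a further condition.

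Three stronger readings are tempting and unsupported:

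- That these events vanish from the report. All AEs and bleeding events are listed, and those that began on study are in the ITO tables.
- That retreatment bleeding is understated by some number of percentage points. Fixing recurrence at 18% would produce a number, but the cited range is 3–84%, and nothing shows how many events are affected, if any.
- That events begun in an earlier episode also drop out. That would need AE tables split by episode. Table 1 allows such a split, but the TEAE periods listed in 2.4.5.1 do not name episode. If episodes are pooled, the subject stays in the overall count.

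**Conclusion.** The inconsistency is real and minor. Two stated rules conflict, and the placement rule gives a result contrary to the SAP's own TEAE definition.

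A subject is missed in a TEAE or bleeding count only if all of these hold: there is a separate AE record; its start date is complete and precedes the recurrence visit; the event worsens or becomes serious on drug; no new record is opened; and the subject has no other on-drug event that counts in the same row. The number affected is unknown and probably small. The safety analyses are descriptive with no systematic testing, and no conclusion is shown to change. The conclusion rests on the wording of SAP 2.1.4.1, 2.4.5.1 and 2.5.4 and on the possibility, not shown, that sites keep one record for an event that worsens.

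**What to change.** Add to SAP 2.4.5.1 that a TEAE is allocated to the analysis period and recurrence episode in which it met the 2.1.4.1 definition, using the date of occurrence, worsening or becoming serious. Take that date from a new AE record opened at the change, or from any recorded date of change or seriousness. Apply the rule to each treated episode separately.

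Where no such date exists, flag in the AE listing the events that started before the episode's first dose and were ongoing at it. Report their count as an upper bound on additional TEAEs, not as TEAEs, since it includes events that never worsened.

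The cost is one sentence, one derivation in the AE dataset and one listing flag. If the eCRF holds no date of change for single records, only the flag and the upper-bound count are possible. The downside is that an event may appear in two periods, which needs a table footnote.

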 - Dosage form: powder for solution for injection; reconstitution with WFI yields solution for injection.
 - Route of administration: i.v. (first dose), s.c. (all subsequent doses).

Study duration:

The anticipated study duration per subject is approximately 3 years.

- Screening/Baseline:

Coinciding with or within 1 month after the Final (28 day) FU visit in Study ALX0681-C301.

Note: for subjects for whom the Final (28 day) FU visit in Study ALX0681-C301 occurred prior to local approval and site activation for this study, a time window of + 1 month after site activation is permitted to complete the screening/baseline visit.
- Assessment period:

Three years, during which twice yearly visits starting from Screening/Baseline will be conducted.

Recurrence of disease (TTP exacerbation/relapse):

A recurrence visit at presentation, a visit on Day 3 of treatment with caplacizumab, weekly visits during treatment with caplacizumab (starting 1 day after the last daily PE), and a recurrence FU visit 1 week after the end of treatment with caplacizumab.

Note: In case the criteria for treatment with caplacizumab are not met (see [Caplacizumab treatment criteria](#)), a recurrence visit at presentation and a recurrence FU visit at 30 days after end of daily PE is to be performed.

Assessments:

- Screening/Baseline and Q6M visits (for timing of assessments, please refer to [Table 1](#))
 - Medical history (including general and TTP-related medical history) and demographics
 - Cognitive assessment: Repeatable Battery for the Assessment of Neuropsychological Status (RBANS) (only in those countries where RBANS is available in the local language[s])
 - Adverse events
 - Concomitant medication
 - Physical examination, vital signs
 - Quality of life assessment: short form 36 (SF36) questionnaire
 - Headache Impact Test (HIT-6™)
 - Laboratory assessments:
 - Hematology (hemoglobin [Hb], hematocrit [Hct], red blood cells [RBC], white blood cells [WBC], platelets)
 - Chemistry (aspartate aminotransferase [AST], alanine aminotransferase [ALT], lactate dehydrogenase [LDH], creatinine, protein, C-reactive protein [CRP], cholesterol)
 - Organ damage marker: troponin (TnI)
 - ADAMTS13 activity
 - PD parameter: vWF:Ag
 - Immunogenicity: ADA panel
 - Urine:
 - Albumin (to calculate albumin creatinine ratio)
- At TTP recurrence (for timing of assessments, please refer to [Table 2](#)):
 - Review of caplacizumab treatment criteria
 - TTP recurrence information

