The sponsor will appoint a DSMB consisting of an independent group of clinical experts who are not participating in the study. They will be supplemented by an independent statistician. The objective of the DSMB will be to review the safety data. The DSMB meetings will be convened every year. This is to review the SAE and mortality information (including the overall number of subjects treated up to that point, rates, and subject-level details). Ad hoc meetings will be determined by the DSMB based on incidence of SAEs. The DSMB will advise the sponsor concerning continuation, modification or termination of the study after every meeting.

The composition, objectives, and role and responsibilities of the independent DSMB will be described in a DSMB charter, agreed with the DSMB members and Sponsor. The DSMB charter will also define and document the content of the safety summaries, and general procedures (including communications).

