3.4.9.1. ADVERSE EVENTS

General information on evaluation and reporting of AEs is provided in section [3.5](#).

All AEs occurring between the time a signed and dated ICF is obtained until completion of the subject's last visit must be documented in the source documents and the eCRF. For adverse events related to injection site reactions, documentation must also include the location of the event.

Criteria for determining whether an abnormal objective test finding (e.g., laboratory, vital signs), a complication of a protocol mandated procedure (e.g., blood draw, injection of study drug), or a change in physical examination findings should be reported as an AE are as follows, but not limited to:

1. Result/finding is associated with accompanying clinical signs and symptoms (new onset or aggravated in severity of frequency from baseline condition), and/or

2. Result/finding requires extra diagnostic testing (other than diagnostic exclusion tests) or medical/surgical intervention, and/or
3. Result/finding would require a change in study drug dosing or discontinuation from the study, significant additional concomitant drug treatment or other therapy, and/or
4. Result/finding leads to any of the outcomes included in the definition of an SAE, and/or
5. Result/finding is considered to be an AE by the Investigator.

Any abnormal test result that is determined to be an error and merely repeating an abnormal test does not require reporting as an AE.

Adverse Event of Interest

In the AE record, the Investigator will need to indicate whether the AE is considered an event indicative of an increased bleeding tendency, manifesting as e.g., overt bleeding, bruising, petechiae, etc.

Exacerbations/Relapses

All exacerbations and relapses must be considered covered by the "another medically important serious event" criterion and must be reported as SAE.

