3.5.2. SERIOUS ADVERSE EVENTS

An SAE is any untoward medical occurrence that meets any of the following conditions:

- Results in death.
- Is life-threatening: the subject is at risk of death at the time of the event. It does not refer to an event that hypothetically might cause death if it were more severe.
- Requires in-patient hospitalization or prolongation of existing hospitalization; an AE associated with a hospitalization or prolongation of hospitalization will not be regarded as an SAE if at least one of the following exceptions is met:
 - The admission results in a hospital stay of less than 12 hours.
 - The admission is pre-planned (i.e., elective or scheduled surgery arranged prior to the start of the study).
 - The admission is not associated with an AE (e.g., social hospitalization for purposes of respite care).

However, it should be noted that invasive treatment during any hospitalization may fulfill the criterion of "medically important" and as such may be reportable as an SAE dependent on clinical judgment. In addition, where local regulatory authorities specifically require a more stringent definition, the local regulation takes precedence.

- Results in persistent or significant disability/incapacity. Disability means a substantial disruption of a person's ability to conduct normal life's functions.
- Results in a congenital anomaly/birth defect.
- Is another medically important serious event as judged by the Investigator, or is defined as requiring intervention to prevent one of the outcomes listed in the definition above (including suspected transmission of an infectious agent by a medicinal product should be reported as an SAE). Other examples of such events are intensive treatment in an emergency room or at home for allergic bronchospasm; blood dyscrasias or convulsions that do not result in hospitalization; or development of drug dependency or drug abuse. Any AE is considered an SAE if it is associated with clinical signs or symptoms judged by the Investigator to have a significant clinical impact.

All exacerbations and relapses must be considered covered by the "another medically important serious event" criterion and must be reported as SAE.

The Investigator or clinical site personnel should notify the contract research organization (CRO) of all SAEs, regardless of relationship to the study drug, within 24 hours of clinical site personnel becoming aware of the event (see Investigator Site File).

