1.3 DETERMINATION OF SAMPLE SIZE

The sample size is not based on statistical considerations but rather on the number of subjects who complete Study ALX0681-C301 (HERCULES) and accept the option to participate in this FU study (ALX0681-C302). All subjects who enrolled in this FU study will be included in the safety and efficacy analyses.

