2.1.4 Safety endpoints

The safety analysis will be based on the reported adverse events and other safety information, such as clinical laboratory data, vital signs and physical examination.

Observation period

The observation period will be divided into 2 non mutually exclusive periods: the on-study period and the recurrence period.

The on-study observation period is defined as the time from informed consent until the end of the study (defined as last protocol planned visit).

The recurrence period is from the start of the recurrence episode, defined as recurrent thrombocytopenia requiring initiation of daily PE, until the last recurrence follow-up visit of that episode. In case of treatment with the IMP, the recurrence period is divided into 2 epochs:

- the **treatment epoch** is defined as the time from the first administration of the IMP to the last administration of the IMP.
- the **residual treatment** epoch is defined as the time from the last administration of the IMP to the last administration of the IMP + 30 days.

The treatment-emergent adverse event (TEAE) period will include both treatment and residual treatment epochs.

In case treatment with the IMP is not initiated during the recurrence episode, there is no subdivision of the recurrence period into the treatment epoch and the residual treatment epoch. The adverse event occurring during that period are not identified as treatment-emergent adverse events.

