The following adverse event summaries will be generated by analysis period for the patients not treated in the recurrence population and for the ITO population.

- Overview of adverse events, summarizing number (%) of participants, the number of events, and the incidence per 100 person months, which will be calculated as: $100 \times (\text{Number of participants with AE}) / (\text{Total number of months observed within analysis period, summed for all participants})$ with any
 - Participants with at least one AE
 - Participants with at least one serious AE

- Participants with at least one AE leading to death
- Participants with at least one PE-related AE (only for the recurrence population)
- Participants with at least one serious PE-related AE (only for the recurrence population)
- Participants with at least one bleeding event, i.e. an event documented as event indicating an increased bleeding tendency
- Participants with at least one bleeding event, based on the Standardized MedDRA Query (SMQ) “Haemorrhage” with exclusion of the PT “TTP”
- Participants with at least one thromboembolic event, based on the SMQ “Embolic and thrombotic events” (arterial, venous, and vessel type unspecified and mixed arterial and venous) with exclusion of the PT “TTP”
- All AE by primary SOC and PT, showing the number (%) of participants with at least 1 AE. The number of events and the number and percentage of participants having an event will be presented.
- AEs will be summarized by SOC, PT and severity. This will be done for each analysis period. The number and percentage of participants having an event will be presented for the worst severity reported for each event.

Analysis of all treatment-emergent adverse events

The following treatment-emergent adverse event summaries will be generated by analysis period for the recurrence population.

- Overview of treatment-emergent adverse events, summarizing number (%) of participants, the number of events, and the incidence per 100 person months, which will be calculated as: $100 \times (\text{Number of participants with AE}) / (\text{Total number of months observed within analysis period, summed for all participants})$ with any
 - Participants with at least one TEAE
 - Participants with at least one serious TEAE
 - Participants with at least one TEAE leading to death
 - Participants with at least one TEAE for which the study drug was interrupted
 - Participants with at least one TEAE for which the study drug was withdrawn

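### The index recurrence is a mandatory SAE that SAP 2.4.5.1 counts for untreated patients but, under the SAP 2.1.4 treatment-emergent window, drops for treated ones, so their SAE overview rows are not comparable

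*SAP*

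**What the plan says.** Protocol 3.5.2, repeated in 3.4.9.1, sets the reporting rule: "All exacerbations and relapses must be considered covered by the" medically-important criterion and reported as serious. The protocol synopsis, under study duration, treats the terms as one: "Recurrence of disease (TTP exacerbation/relapse").

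SAP 2.3.2 admits to the recurrence population only patients with at least one recurrence in this study. SAP 2.1.4 adds: "The recurrence period is from the start of the recurrence episode, defined as recurrent thrombocytopenia requiring initiation of daily PE". For episodes treated with caplacizumab, the same section starts the treatment-emergent period at the first dose and ends it 30 days after the last. Untreated episodes have no such subdivision.

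SAP 2.4.5.1 applies a different filter to each group: "Tables on the recurrence population will include only adverse events that occurred during the recurrence period, treatment-emergent (for patients who received the IMP"), and non-treatment-emergent events for those who did not receive it. The overview for untreated patients and for the ITO population has the row "Participants with at least one serious AE"; the treated overview has the matching serious TEAE row. Neither removes TTP. The SMQ-based bleeding and thromboembolic rows in the same overviews do exclude the preferred term TTP.

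On monitoring, Protocol 3.1.1 says: "Ad hoc meetings will be determined by the DSMB based on incidence of SAEs".

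**The concern.** The event that qualifies a patient for the recurrence population is a reportable SAE by rule. One column of the safety overview takes it in and the other is built to leave it out. A reader comparing treated with untreated recurrences would then see a lower SAE percentage under caplacizumab that owes nothing to the drug.

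The safety of repeated use is a stated objective (SAP 1.2), and SAP 2.4.5 names treated and not treated with IMP as the groups for presenting adverse events in this population. Nothing is tested, so these side-by-side percentages are the safety result. Excluding TTP from the SMQ rows removes disease events there; the serious rows have no equivalent.

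**Working it through.** There is no design figure to reproduce: "The sample size is not based on statistical considerations", and no expected SAE rate is given. The check follows the definitions and then works through simple proportions.

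**Where the index event goes**

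1. Every recurrence is an SAE, and membership of the population requires a recurrence. So 100% of members have at least one reportable SAE.
2. Untreated: the recurrence period opens with the event, so it counts. One exception: SAP Table 2 opens the period at the recurrence visit date, so an SAE dated to earlier symptoms would fall outside.
3. Treated: caplacizumab is started only for a diagnosed recurrence that needs daily PE (Protocol 3.2.3). Onset therefore precedes the first dose and lies outside the SAP 2.1.4 window when date and time are complete.
4. Several rules can bring the treated index event back in:
   - SAP Table 1 opens the Treatment period at the recurrence visit, not at the first dose.
   - SAP 2.1.4.1 counts events that worsened or became serious inside the window.
   - SAP 2.4.5.1 treats an incomplete onset as treatment-emergent unless there is definite information otherwise.
   - SAP 2.5.3 counts everything from the recurrence visit onward if the first-dose time is missing.

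**Size in the recurrence population**

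The documents give none of these three inputs, so all are assumptions:
- s: share of patients with an SAE other than the index recurrence, taken as equal in both groups and independent of how the index event is dated.
- q: share of untreated index SAEs that fall inside the period.
- c: share of treated index SAEs classed as treatment-emergent.

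Untreated = 1 - (1-q)(1-s). Treated = 1 - (1-c)(1-s). Gap = (q-c)(1-s).

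| q | c | s = 20%: untreated / treated / gap | s = 55%: untreated / treated / gap |
|---|---|---|---|
| 1 | 0 | 100 / 20 / 80 | 100 / 55 / 45 |
| 1 | 0.5 | 100 / 60 / 40 | 100 / 77.5 / 22.5 |
| 1 | 1 | 100 / 100 / 0 | 100 / 100 / 0 |
| 0.9 | 0 | 92 / 20 / 72 | 95.5 / 55 / 40.5 |
| 0.7 | 0 | 76 / 20 / 56 | 86.5 / 55 / 31.5 |
| 0.9 | 1 | 92 / 100 / -8 | 95.5 / 100 / -4.5 |

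The Phase II SAE proportions in Protocol 1.2.4, 57.1% and 51.4%, give gaps of 42.9 and 48.6 points at q = 1 and c = 0. They are illustrations only, since the protocol does not say whether recurrences were counted as SAEs there.

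If the index event is left out of both columns, both show s and the gap is 0 at any s.

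**ITO population**

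A recurrence adds to the any-SAE row only those with no other SAE. That is r(1-s), with r the recurrence proportion and independence assumed. At the 18% median in Protocol 1.1: 18 × 0.80 = 14.4 points at s = 20%, and 18 × 0.45 = 8.1 points at s = 55%.

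**DSMB**

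The share of SAE subjects who have a recurrence is r/(r + s(1-r)). It exceeds one half only when s < r/(1-r). At r = 18% this is 0.18/0.82 = 22.0%.

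**The case against.** The strongest defence is that the plan makes no formal comparison. All analyses are descriptive, and the two groups have different overviews (AE and TEAE) over different analysis periods. The untreated group is also selected: it includes pregnant patients and those with earlier severe hypersensitivity. Serious events are tabulated by SOC and preferred term, so TTP has its own line. Treatment-related SAEs, bleeding and hypersensitivity are summarised separately, pretreatment events are to be described separately, and SAP 2.4.4.3 reports recurrences as efficacy.

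Much of this stands. It means that a drug-related signal can still be found, and a reader who inferred that the SAE data cannot show one would go too far. But it only partly offsets the problem. The SOC/PT tables use the same group-specific filter, so their totals carry the same asymmetry, and the overview rows allow no separation at all.

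Three other strong readings are not supported:

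- **Treated patients never show the event, or the gap is a full 100 points.** The re-entry rules listed above contradict the first. The second needs s = 0 as well as c = 0. A new exacerbation on treatment, or a relapse within 30 days of the last dose, is also a legitimate serious TEAE.
- **The ITO serious row merely restates the recurrence count.** It counts any SAE, and recurrence adds r(1-s), not r.
- **The DSMB trigger mainly tracks relapse.** Protocol 3.1.1 sets no numeric trigger, gives the board subject-level details, and leaves the summaries to a charter. Whether recurrences dominate depends on rates that the documents do not give. What can be said is that recurrences inflate the incidence the board sees, and the protocol asks for no split.

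**Conclusion.** The point holds for the AE and SAE rows of the recurrence-population tables. On the SAP 2.1.4 definition with complete onset data, the untreated column contains the index SAE and the treated column does not. The built-in gap is then 100(1-s) points, about 45 to 80 for s between 55% and 20%. It shrinks to about 0 if every treated index event is classed as treatment-emergent, and reverses slightly if some untreated events are also dated before the recurrence visit.

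That range is itself the difficulty: the treated percentage can lie anywhere from s to 100% according to which SAP passage the programmer follows and whether an onset time was recorded. The figures assume a common s, independence, and an index SAE dated to the episode it opens. The direction at c = 0 does not depend on the value of s, provided s is below 100%.

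This is a defect of presentation that should be corrected before the tables are produced. It does not invalidate the study's safety data.

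**What to change.** In SAP 2.4.5.1:

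- Derive a flag in the AE dataset for the index recurrence of each episode.
- Present the AE and SAE overview rows and SOC/PT tables without the flagged event in both the treated and not-treated groups, and show index recurrences on a separate line.
- Do not do this by excluding the preferred term TTP. Protocol 1.2.4 reports that 7 of 8 first-month relapses in the Phase II caplacizumab arm came 4-10 days after stopping, and a blanket exclusion would delete such events. A recurrence inside the treatment-emergent window of an earlier treated episode should remain a serious TEAE of that episode, even where it is the flagged event of the one it opens.
- Reconcile the start of the treatment-emergent period in SAP 2.1.4 with the start of the Treatment period in SAP Table 1.
- In the ITO overview, add an SAE row excluding recurrences beside the all-SAE row.

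For the DSMB, show SAE incidence with and without recurrences. Leave the ad hoc meeting rule and the SAE reporting requirement as they are.

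The cost is one derived flag, a few table rows and a clarified definition, with no new data collection.
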